#### 6.1.1.1. Sensitivity/Supplementary Analyses

### 6.2. Secondary Endpoint(s)

#### 6.2.1. CDASI Activity and Damage Scores

##### 6.2.1.1. Main Analysis

- Estimand strategy: E1.

- Analysis sets: Skin Analysis Set and Muscle Analysis Set.
- Analysis methodology: Each CDASI endpoint (including CFB CDASI activity score, CFB CDASI damage score, absolute value of CDASI activity score, and absolute value of CDASI damage score) will be analyzed using LANCOVA including data from baseline to Week 52 with week as a fixed effect and baseline score as a covariate and an unstructured covariance matrix ([Section 5.2.1](#)).
- Intercurrent events and missing data: Data after study drug discontinuation will be excluded; intermediate missing values will not be imputed.
- The sample size, mean, standard deviation, median, minimum, and maximum at the baseline and postbaseline visits for observed CDASI scores and change from baseline CDASI scores will be presented for each cohort for each CDASI endpoint.
- For each CDASI endpoint, the least-squares (LS) means and the 90% confidence interval for the LS means will be presented and plotted for all postbaseline visits.

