6.8.3.1. Guidance for Investigators

During the course of the study, those participants who experience a severe flare requiring new or increased doses of immunosuppressants (including new or increased doses of corticosteroids beyond what is permitted), will be discontinued from the treatment period of the study and placed in the follow up period, and therefore, will receive no further study intervention. Rescue therapy may be administered as clinically necessary.

See [Appendix 11 \(Section 10.11\)](#) for further guidelines for corticosteroid use.

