6.8.4. Rescue Medicine

If the participant requires the addition of higher DMARD doses or an additional DMARD for a flare or persistent increase in dermatomyositis activity, then the participant should be discontinued from the treatment period but complete the follow-up visits. High dose oral corticosteroids (>100 mg/day prednisone, or equivalent) or pulse IV doses, or any IV or IM steroid injection would exclude the participant for further treatment in the study.

See [Appendix 11 \(Section 10.11\)](#) for further guidelines for rescue medication.

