Any participant meeting discontinuation criteria must enter follow-up with their first follow-up visit occurring 1 week after their last dose whenever possible, until the event has returned to normal or baseline levels or is deemed clinically stable. The procedures scheduled for the early withdrawal visit will be performed on the last day the participant takes the study intervention or as soon as possible thereafter. The only exception to this is when a participant specifically withdraws consent for any further contact with him/her or persons previously authorized by the participant to provide this information.

Participants will be followed post drug discontinuation for 5 terminal half-lives. Additional follow-up visits may occur as needed until any clinically relevant abnormalities or adverse events have resolved, returned to a baseline state, or are deemed clinically stable.

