### 5.3. Methods to Manage Missing Data

- In the longitudinal modeling (LANCOVA) of repeated measures of continuous outcomes (both efficacy measures and covariates) it is assumed that missing data are generated by the “missing at random” mechanism and, therefore imputation of the missing data is not necessary.
- In all data presentations of PK outcome (except listings), concentrations below the limit of quantification (BLQ) will be set to zero. (In listings BLQ values will be reported as “<LLQ”, where LLQ will be replaced with the value for the lower limit of

quantification). In summary tables and plots of median profiles, statistics will be calculated having set concentrations to missing if concentration measurement was not done or sample was not collected.

- The PK summary statistics will not be presented at a particular time point if more than 50% of the PK data are missing.
- Immunogenicity assay titers will be used to determine incidence for ADA and NAb. If a titer value is missing data imputation will not occur and missing values will be represented by NC (ie, not-calculated).
- For other endpoints, statistical analyses will be based on available data. Missing data will not be imputed.

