### 6.2.2.2. Sensitivity and Supportive Analyses

- *Supportive*: the frequency and proportions of patients achieving minimal improvement (TIS $\geq$ 20), moderate improvement (TIS  $\geq$ 40) and major improvement (TIS  $\geq$ 60) will also be reported for each postbaseline visit. 90% CIs will also be provided using Chan and Zhang's exact CI method.

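### Week 52 CDASI and TIS results are likely to look too favourable if treatment-ending flares persist, and no planned analysis departs from missing at random

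*SAP*

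**What the plan says.** **Who stops.** Protocol 6.8.3.1 covers "those participants who experience a severe flare requiring new or increased doses of immunosuppressants", including corticosteroids beyond the permitted level; these participants "will be discontinued from the treatment period of the study and placed in the follow up period". Protocol 6.8.4 adds that if a flare needs a higher DMARD dose or a further DMARD, "then the participant should be discontinued from the treatment period but complete the follow-up visits". Protocol 10.11.2.4 says much the same for non-steroid agents.

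**What is dropped.** SAP 6.2.1.1 (CDASI) states: "Data after study drug discontinuation will be excluded; intermediate missing values will not be imputed". SAP 6.2.2.1 (TIS) and 6.2.3.1 (core set measures) repeat the rule, and the E1 and E2 definitions (Protocol 9.1.1.2, SAP 2.1.2) censor scores from the point of withdrawal from treatment.

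**What is assumed.** SAP 5.3 assumes MAR for the longitudinal model (LANCOVA), so "imputation of the missing data is not necessary". For other endpoints, "statistical analyses will be based on available data. Missing data will not be imputed".

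**What else is planned.**
- Protocol 9.3.3 gives an ANCOVA on baseline and Week 52 observations only. SAP 5.2.1 names ANCOVA for sensitivity analyses, but SAP 6.2.1.2 and 6.2.2.2 do not list it.
- SAP 6.2.1.2 repeats the same CDASI model on the Pooled Skin Analysis Set.
- SAP 6.2.2.2 reports "the frequency and proportions of patients achieving minimal improvement", and likewise moderate and major improvement, with no stated denominator.

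**Early termination.** Both Schedules of Activities mark CDASI at the early-termination visit; the muscle schedule also marks the TIS components. On timing, Protocol 10.10.2 says: "The procedures scheduled for the early withdrawal visit will be performed on the last day the participant takes the study intervention", and the sentence goes on to allow a later date. The SAP 9.1 window table has no early-termination row.

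**The concern.** A severe flare is a treatment failure on the scale that CDASI and TIS measure. The plan makes it a reason to stop and then removes what follows from the data. MAR is reasonable only if the retained scores explain who stops. On-treatment CDASI is scheduled at Weeks 12, 24, 36, 48 and 52, so a sudden flare between visits may leave no trace in them. The model then predicts Week 52 for that participant as if the flare had not happened.

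The responder proportions are more exposed. With an available-data rule, a participant who stops for a flare leaves the denominator altogether instead of counting as a non-responder.

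The study has one open-label arm, so the Week 52 means and responder proportions carry the durability message with no control group to share the bias.

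**Working it through.** The plan states no figure to reproduce: about 30 participants roll over, with no power calculation, effect size or dropout rate. The check concerns direction and order of size.

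**1. Approximation.** Let p be the proportion stopping for flare, D the shift in CDASI activity that the flare adds at Week 52, and m the mean without flare. Suppose the flare score is lost, the flare persists and flare risk is unrelated to earlier scores.
- Week 52 mean with flares counted: m + pD.
- MAR estimate: about m.
- Bias: about -pD (negative looks better).

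This gives 0.10 × 5 = 0.5, 0.20 × 10 = 2.0 and 0.30 × 20 = 6.0 points.

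**2. Simulation.** From the documents: SD 9.14 (Stage 1 active arm, CDASI activity change at Week 12, Protocol 4.3) and the five on-treatment CDASI visits. Assumed: visit correlation 0.6, p of 10-30%, D of 5-20 points lasting to Week 52, and flare risk independent of earlier scores. There were 20,000 participants per scenario. The MAR estimate is maximum likelihood with visit means and unstructured covariance, without the baseline covariate. The completer mean at Week 52 stands in for the ANCOVA.

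| p, D | Flare score lost: MAR / completer | Flare score kept: MAR / completer |
|---|---|---|
| 10%, +5 | -0.45 / -0.47 | -0.22 / -0.38 |
| 20%, +10 | -2.01 / -2.01 | -0.92 / -1.52 |
| 30%, +20 | -5.96 / -5.93 | -2.52 / -4.40 |

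The MAR column follows pD when the score is lost and is roughly halved when it is kept. The completer analysis is equally biased in the first case and more biased in the second, so it is no safeguard. With n = 15 (20%, +10) the mean MAR bias is -2.0 with the score lost and -0.8 with it kept.

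**3. TIS mean.** Assumed: SD 20, mean without flare 20 or 40 before clipping to 0-100, and TIS of 0 after a flare. Bias is +2.2 to +11.9 points with the flare score lost (+8.0 at 20% and mean 40) and +1.1 to +5.5 with it kept.

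**4. TIS responders.** With r responders among n dosed and d stopped, the available-data proportion is r/(n - d), against r/n if stops count as non-response. The inflation factor is n/(n - d). As an invented illustration, n = 15, d = 3 and r = 8 give 8/12 = 67% against 8/15 = 53%, a factor of 15/12 = 1.25.

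**5. Does the early-termination score enter?** Five on-treatment CDASI windows of 7 days cover 35 of the 367 days from Day 2 to Day 368, or 9.5%. A score taken on a 4-weekly dosing day would fall in that visit's window, but the SAP does not say whether a CDASI score at, say, Week 16 enters the model.

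**6. Scale.** The 90% CI half-width for a mean is t × 9.14/√n: 1.761 × 2.360 = 4.2 at n = 15, and 1.699 × 1.669 = 2.8 at n = 30.

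**The case against.** **The estimand is hypothetical, so censoring follows from it.** This stands for keeping the main analysis. But E1 and E2 remove dropout, not the flare: a participant who flared and stayed would still have had the flare score. Protocol Section 3 and SAP Table 2 also name only study withdrawal as the intercurrent event, and Protocol 7.1 says that stopping drug is not study withdrawal.

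**A reader might infer that the flare score is always excluded.** The documents do not support this. The rule removes data after discontinuation, that date is undefined, and Protocol 10.10.2 lets the visit fall on the last dosing day. A flare score at a scheduled visit before the stop is kept.

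**A reader might infer that MAR must fail.** That is too strong. Protocol Section 2 describes symptoms that come on suddenly or gradually and that wax and wane. Gradual worsening would show in earlier scores, and flares that resolve by Week 52 leave little bias.

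**A reader might infer that the means describe only participants who did not fail.** They do not: LANCOVA keeps each dropout's earlier on-treatment scores. Protocol Appendix 11 also describes steroid rescue without a stated stop, so not every flare ends treatment. The available-data responder proportions do lose later dropouts.

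**The size restates its assumptions.** This stands. The Stage 1 difference of 14.82 cannot serve as a flare size, because it is an active-minus-placebo contrast at Week 12.

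**The consequence is limited.** These are secondary, estimation-only endpoints, and the rule does not touch the primary safety endpoint. Sample size by visit and discontinuation counts will show attrition, but they do not correct for it.

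**Conclusion.** The point holds in a conditional form. Severe flares needing extra immunosuppression end treatment, later scores are excluded, and every planned analysis relies on MAR, completers or available data. Week 52 CDASI and TIS means, and above all the TIS responder proportions, are likely to be biased towards benefit if flares persist and earlier scores did not foreshadow them. The direction was the same in every scenario run.

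The size is driven by assumption. For CDASI it is 0.5 to 6 points with the flare score lost and 0.2 to 2.5 with it kept, for 10-30% stops and a 5-20 point shift. At the middle setting (2.0 points) it is about half the 90% CI half-width for 15 participants; at the extreme it exceeds that half-width. It is near zero if flares resolve. Whether the early-termination score is excluded cannot be settled from the text, and that is itself a gap. This is a cheap improvement, not a flaw in the primary objective.

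**What to change.** Keep the E1/E2 LANCOVA as the main analysis, and make these changes:

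- **SAP 6.2.2.2.** Report TIS 20/40/60 proportions with all dosed Muscle Analysis Set participants as denominator, counting discontinuation for flare, lack of efficacy or rescue as non-response. Show them beside the available-data version, with both denominators stated.
- **SAP 6.2.1.2.** Add one Week 52 CDASI sensitivity analysis that departs from MAR for flare or rescue discontinuations. Examples are carrying the early-termination score to Week 52, or a delta adjustment over a stated range. Carrying the score forward assumes that the flare persists, so it should be labelled as a sensitivity analysis only.
- **Definitions.** Define the discontinuation date. State whether, and at which visit, an early-termination score taken on or before that date enters the model. Reconcile study withdrawal (Protocol Section 3, SAP Table 2) with treatment stop (Protocol 9.1.1.2, SAP 6.2.1.1).
- **Protocol consistency.** The passages on corticosteroid use during treatment (6.8.3.1, 6.8.4 and Appendix 8 Table 4 against 10.11.2.1 and 10.11.2.3) differ on what ends treatment and must be reconciled, because they decide how many participants the censoring rule reaches.

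The analysis changes cost SAP wording and two extra tables. They need no new data, since the early-termination assessments are already scheduled. The downside is a less favourable supportive estimate. Moving early-termination scores taken after the stop into the main model is not proposed, because that would change the censoring rule of the stated estimands.

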#### 6.2.1.2. Sensitivity and Supportive Analyses

- *Supportive*: For each CDASI endpoint, the analysis of [Section 6.2.1.1](#) will be repeated using the Pooled Skin Analysis Set.

#### 6.2.2. TIS

##### 6.2.2.1. Main Analysis

- Estimand strategy: E2.
- Analysis sets: Muscle Analysis Set.
- Analysis methodology: The TIS will be analyzed using LANCOVA including data from baseline to Week 52 with week as a fixed effect and an unstructured covariance matrix ([Section 5.2.1](#)).
- Intercurrent events and missing data: Data after study drug discontinuation will be excluded; intermediate missing values will not be imputed.
- The sample size, mean, standard deviation, median, minimum, and maximum at the baseline and postbaseline visits for the TIS will be presented.
- The LS means and the 90% confidence interval for the LS means will be presented and plotted for all postbaseline visits.

### 6.2.2.2. Sensitivity and Supportive Analyses

- *Supportive*: the frequency and proportions of patients achieving minimal improvement (TIS $\geq$ 20), moderate improvement (TIS  $\geq$ 40) and major improvement (TIS  $\geq$ 60) will also be reported for each postbaseline visit. 90% CIs will also be provided using Chan and Zhang's exact CI method.

### 6.2.3. CSMs

#### 6.2.3.1. Main Analysis

- Estimand strategy: E2.
- Analysis sets: Muscle Analysis Set.
- Analysis methodology: The CFB in each CSM (including PhGA, PtGA, MMT-8, HAQ-DI, global extramuscular disease activity assessment from the MDAAT, and most abnormal muscle enzyme) will be analyzed using LANCOVA including data from baseline to Week 52 with week as a fixed effect and baseline score as a covariate and an unstructured covariance matrix ([Section 5.2.1](#)).
- Intercurrent events and missing data: Data after study drug discontinuation will be excluded; intermediate missing values will not be imputed.
- The sample size, mean, standard deviation, median, minimum, and maximum at the baseline and postbaseline visits for the TIS will be presented.
- The LS means and the 90% confidence interval for the LS means will be presented and plotted for all postbaseline visits.

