8.1.2. Total Improvement Score (TIS)

There are 6 core set measures that comprise the total improvement score. These components are:

- PhGA, VAS (see [Section 8.1.2.1](#));
- PtGA (see [Section 8.1.3.4](#));
- MMT-8 score (see [Section 8.1.2.2](#));
- HAQ- DI score (see [Section 8.1.3.3](#));
- MDAAT Global Extramuscular Disease Activity ([Section 8.1.2.3](#) and
- The participant's most elevated muscle enzymes.

The total improvement score is the sum of all 6 improvement scores associated with the change in each core set measure.

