	
 
Absolute values and change from baseline of CDASI activity and CDASI damage scores at all scheduled timepoints.
 
TIS score at Week 52 and at intermediate scheduled timepoints for participants who entered from Stage 3 of Protocol C0251002.
 
Change from baseline in the CSMs of the TIS including PhGA, PtGA, MMT-8, HAQ-DI, muscle enzymes, and MDAAT at Week 52 and at intermediate scheduled timepoints.
 
	
Analysis Set (see details in Section 4).
 
 
These additional CDASI endpoints will be analyzed using E1 at all scheduled timepoints.
 
E2: This estimand uses a hypothetical estimand strategy (ICH E9 addendum) estimating the mean effect of PF-06823859 in the absence of intercurrent events (study withdrawal). This is the mean TIS at Week 52 for all randomized and dosed participants included with non-missing baseline score in the Muscle Analysis Set (see details in Section 4).
 
The endpoints for the CSM of the TIS will be analyzed using E2 at Week 52 and all intermediate scheduled timepoints.
 

Tertiary/Exploratory:	Tertiary/Exploratory:	Tertiary/Exploratory:

 
To characterize pharmacokinetics (PK) of PF-06823859.
 
To characterize pharmacodynamics (PD) effects of PF-06823859.
 
To evaluate immunogenicity of PF-06823859.
 
To evaluate the effect of PF-06823859 on suicidality assessment over time in participants with active DM.
 
To evaluate the effect of PF-06823859 on SF-36
 
	
 
Plasma concentrations of PF-06823859.
 
Absolute values and change from baseline in the values of selected biomarkers at all scheduled time points.
 
Incidence of ADA and NAb.
 
Absolute values and change from baseline values of Columbia-Suicide Severity
 
	
 
Not applicable.
 

(v2 acute) and EQ-5D-5L PROs.	Rating Scale (C-SSRS) at all scheduled time points.  

Absolute values and change from baseline in the values of PROs including SF-36 (v2 acute) and EQ-5D-5L at all scheduled timepoints.

	
--------------------------------------	--	--

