**Figure 1. Study Schema**

### **3. ENDPOINTS AND BASELINE VARIABLES: DEFINITIONS AND CONVENTIONS**

For the skin cohort (ie, participants entering C0251008 from Amended Stage 2 of C0251002), the major efficacy analyses assess changes in the modified CDASI *activity* and *damage* scores. The details of the calculation of these scores are presented in [Section 9.2](#).

For the muscle cohort (ie, participants entering C0251008 from Stage 3 of C0251002), the major efficacy analyses assess changes in the modified CDASI activity and damage scores and changes in the TIS and the CSM. The details of the calculation of the TIS are presented in [Section 9.3](#).

Safety assessments for the primary endpoint will be reported for all participants and by cohort. Efficacy assessments will generally be reported by cohort.

Unless specifically stated otherwise, the baseline value for all assessments is defined as the last non-missing measurement collected prior to the first administration of study drug at Day 1. Change from baseline is defined as the value at a specific visit minus the value from baseline.

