### **3.2.2. TIS**

The TIS is a continuous measure ranging from 0 to 100 that assesses disease activity relative to baseline. By definition, all participants have a TIS of 0 at baseline. A TIS  $\geq 20$  represents minimal improvement, TIS  $\geq 40$  represents moderate improvement, and TIS  $\geq 60$  represents major improvement.

Six CSMs contribute to the TIS, including the PhGA, PtGA, MMT-8, HAQ-DI, global extramuscular disease activity assessment from the MDAAT, and muscle enzymes. The TIS is the sum of all 6 improvement scores associated with the change in each CSM.

[Appendix 9.3](#) provides full details on the computation of the TIS and each CSM. The absolute values and CFB in each CSM will be assessed.

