### 3.2.2.6. Muscle Enzymes

Five muscle enzymes are assessed for the TIS, including aldolase, alanine aminotransferase, aspartate aminotransferase, lactate dehydrogenase, and creatine kinase. The most abnormal serum muscle enzyme among these is used in the computation of the muscle enzyme CSM of the TIS.

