#### 6.3.2. PD Endpoints, including Selected Biomarkers (hsCRP, total IFN $\beta$ )

- Analysis population: biomarker analysis population.
- Analysis time points: all visits with samples taken.
- Analysis methodology: summary statistics. The change from baseline may also be investigated by applying the LANCOVA model (as described in [Section 5.2.1](#)). The

log-transformation of the outcomes may be applied to the original observations after analysis of the distribution of observed data.

- Descriptive statistics for absolute values, change from baseline, percent change from baseline will include sample size, mean, standard deviation, median, minimum and maximum by visit.
- Presentations for biomarker concentrations will also include:
  - A listing of all concentrations sorted by participant ID, cohort, and nominal time post-dose. The concentration listing will also include the actual times. Deviations from the nominal time will be given in a separate listing.
  - A summary of concentrations by nominal time post-dose, where the set of statistics will include n, mean, median, standard deviation, CV, minimum, maximum and the number of concentrations above the lower limit of quantification.
  - Median concentrations time plots (semi-log scale) against nominal time post-dose.
  - Mean concentrations time plots (semi-log scale) against nominal time post-dose.
  - Individual concentration time plots by participant (semi-log scales) against actual time post-dose will be presented.

Additional biomarkers may be reported an additional exploratory analysis report.

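### The muscle-enzyme core set measure is modelled as a plain difference in whichever enzyme is most abnormal, so its mean has no common scale

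*SAP*

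**What the plan says.** The muscle-enzyme measure is one of the named secondary endpoints: SAP Table 2 lists change from baseline in "PhGA, PtGA, MMT-8, HAQ-DI, muscle enzymes, and MDAAT at Week 52 and at intermediate scheduled timepoints".

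Three parts of the SAP determine how it is analysed:

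- **Which enzyme.** Section 3.2.2.6: "Five muscle enzymes are assessed for the TIS, including aldolase, alanine aminotransferase, aspartate aminotransferase, lactate dehydrogenase, and creatine kinase". It continues: "The most abnormal serum muscle enzyme among these is used in the computation of the muscle enzyme CSM of the TIS". Protocol Section 8.1.2 speaks of the participant's "most elevated muscle enzymes". Neither gives the metric for ranking the enzymes, or says whether the choice is made once or at every visit.
- **What change means.** Section 3: "Change from baseline is defined as the value at a specific visit minus the value from baseline".
- **The model.** Section 6.2.3.1: the change in each measure, "and most abnormal muscle enzyme) will be analyzed using LANCOVA including data from baseline to Week 52", with week as a fixed effect, the baseline score as covariate and an unstructured covariance matrix. LS means and 90% CIs are reported at every postbaseline visit. Section 6.2.3.2 adds means and SDs of the absolute values.

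Section 5.2.1, to which 6.2.3.1 refers, gives no scaling for the core set measures. A log scale appears only for PD endpoints in Section 6.3.2, and only as an option: "log-transformation of the outcomes may be applied to the original observations after analysis of the distribution of observed data". Section 3.2.2 says that Appendix 9.3 "provides full details on the computation of the TIS and each CSM", but the table in that appendix is withheld as copyrighted.

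**The concern.** The other five core set measures each use one instrument that is the same for every participant. The enzyme measure may be creatine kinase (CK) in one person and aldolase in another. If their reference ranges differ widely, a plain difference weights participants by which analyte was chosen as well as by how much they changed.

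The same fault reaches the covariate. Two participants who are equally abnormal relative to their reference range can enter with very different baseline values, so the common slope partly separates analytes when it should adjust for severity. One covariance matrix is then fitted to the mixture.

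At stake is the main analysis of one named secondary endpoint. Its LS mean and interval may reflect one or two people, and the mean may point the wrong way.

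**Working it through.** The plan states no figure for this endpoint, so there is none to reproduce. The check applies the SAP's own definition of change to worked cases.

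**From the documents:** five candidate enzymes (SAP 3.2.2.6); change = visit value − baseline value (SAP 3); about 30 participants over both cohorts, with no size given for the muscle cohort (Protocol 9.5).

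**Assumed, because the documents give no units or reference ranges:** ULN of CK 200 (range 150–300), aldolase 8 (range 6–10), LDH 250, ALT 40 and AST 40, all in U/L; cohorts of 10 to 20.

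**Step 1. Weight of one participant.** Take the same relative fall, from 5×ULN to 1×ULN.
- CK: 1000 → 200, change −800.
- Aldolase: 40 → 8, change −32.
- Ratio 800/32 = 25, which is the ratio of the ULNs (200/8). Over the assumed ranges it runs from 150/10 = 15 to 300/6 = 50.

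**Step 2. Enzyme fixed at baseline, n = 10.** Nine aldolase participants go from 40 to 8 and one CK participant goes from 1000 to 1500.
- Plain change: (500 − 9×32)/10 = (500 − 288)/10 = **+21.2**.
- In multiples of ULN: (2.5 − 9×4)/10 = **−3.35**.
- On the log scale: (ln 1.5 + 9 ln 0.2)/10 = (0.405 − 14.485)/10 = −1.408, which back-transforms to 100×(e^−1.408 − 1) = −75.5%.
- The plain mean turns positive once the single CK rise exceeds 288 U/L.
- Holding the same multiples of ULN, the plain mean is (2.5×CK ULN − 36×aldolase ULN)/10. It runs from (375 − 360)/10 = +1.5 to (750 − 216)/10 = +53.4 over the assumed ranges.

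With complete data and LS means taken at the average baseline, the model's LS mean at a visit equals this simple mean, so the covariate does not remove the effect.

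**Step 3. Enzyme re-selected at each visit, one participant.** All five enzymes fall: CK 150 → 140, aldolase 40 → 7, ALT 60 → 38, AST 70 → 38, LDH 320 → 275. The most abnormal is aldolase at baseline (40/8 = 5.0×ULN) and LDH at Week 52 (275/250 = 1.1×ULN). Recorded change: 275 − 40 = **+235**. With aldolase kept, it is 7 − 40 = −33.

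**Step 4. How often the mean is wrong-signed.** Simulation with 4000 runs per setting. Baseline values are log-normal around 1.2×ULN, and every enzyme has the stated typical (geometric mean) fall. The table shows the proportion of runs with a mean change above zero, for n = 15:

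| Fall | SD of log change | Plain, fixed | Plain, re-selected | log(value/ULN), fixed |
|---|---|---|---|---|
| 20% | 0.5 | 27.2% | 59.3% | 4.8% |
| 30% | 0.5 | 11.5% | 41.7% | 0.4% |
| 50% | 0.3 | 0% | 1.6% | 0% |

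Over n = 10–20, falls of 20–50% and SD 0.3–0.5, the ranges are 0–30%, 1–60% and 0–7.9%. The two fixed-enzyme columns isolate the choice of scale. The re-selected column also carries the upward pull of taking the highest of five noisy values again at follow-up.

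**The case against.** The strongest objection is that part of the plan cannot be read. Section 3.2.2 sends the reader to Appendix 9.3 for the computation of each core set measure, and its table is withheld. If that table fixes the enzyme or puts it on a common scale, the subtraction in Section 3 would act on that value. This stands as a limit: one cannot say that the plan lacks such a rule. It does not dispose of the point. The visible title of the table describes response criteria for improvement, and nothing readable says that it replaces the Section 3 difference in the 6.2.3.1 model.

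A reader might also infer more than the documents support:

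- **That enzymes in different units are averaged.** No units are given, and the examples above put every enzyme in U/L. The argument needs only different reference ranges.
- **That the enzyme is re-selected at each visit.** That is one of two possible readings. Step 2 does not depend on it.
- **That the result will be wrong-signed, or will be driven by one or two people.** Step 2 is a constructed case, the mix of enzymes is unknown, and the simulated rates rest on assumed distributions. With a fixed enzyme and large, uniform falls the rate is near zero.
- **That the TIS is compromised.** Nothing readable shows this.

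Mitigations are planned as well. Section 3.3.1 includes the individual muscle enzymes among the PD biomarkers, with absolute value and change for each. Section 6.2.3.2 reports improvement categories at Week 52, and medians and ranges by visit. These would help a reader notice a distorted mean, but they do not repair the LS mean and interval that form the main analysis.

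**Conclusion.** The point holds in a limited form. The readable rule averages plain differences from analytes that may differ between participants, under one baseline slope and one covariance matrix. The resulting mean has no clear interpretation, whichever selection rule applies. That conclusion needs only that participants' selected enzymes differ and that reference ranges differ.

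The size rests on assumption. For the same relative change, a CK participant carries about 25 times the weight of an aldolase participant (15 to 50 over the assumed ULNs). A wrong sign is possible, as +21.2 against −3.35×ULN shows, but its frequency cannot be read from the documents.

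The consequence is bounded: one of six core set measures, secondary, in a single-arm extension with no hypothesis testing. It remains conditional on Appendix 9.3 not already setting a different rule. It is worth correcting before database lock because the remedy is cheap.

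**What to change.** In SAP 6.2.3.1, state for the muscle-enzyme measure that:

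- the enzyme is chosen once, at Day 1, as the highest multiple of ULN among the five, and kept at all visits;
- the outcome is change in log(value/ULN), with the log baseline as covariate and LS means back-transformed to percent change. Another common relative scale, such as percent change, would also remove the main fault;
- the absolute-value summaries in 6.2.3.2 use multiples of ULN;
- the single-enzyme summaries already planned under Section 3.3.1 serve as support.

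If Appendix 9.3 already contains such a rule, cite it in 6.2.3.1 and say that it overrides the Section 3 difference for this measure.

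The cost is a few lines of SAP text and one derivation using laboratory reference ranges. All five enzymes are already in the protocol's laboratory table (Appendix 2), so no new data are needed. SAP Section 2 ties protocol amendments to major changes in the primary endpoint, and this is not one.
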